1.1 Background

The treatment of prostate cancer results in several known sexual dysfunctions, including erectile dysfunction, orgasmic dysfunction, ejaculatory dysfunction, penile curvature (Peyronie's disease), and reduced penile length. Although all forms of prostate cancer treatment are associated with many of these changes, prostatectomy currently has the most data available on sexual function outcomes. Among the dysfunctions, loss of penile length is often one that results in significant distress and bother to patients. Beyond the esthetic concerns, reduced penile length may lead to inability to participate in sexual intercourse, difficulty with future interventions to restore erectile function (placement of a penile prosthesis), and lead to worsened urinary hygiene (leak urine onto self, leading to yeast infections and other issues).

Penile traction therapy (PTT) is currently the best available treatment to maintain or restore lost penile length due to conditions that reduce length.¹ Prior studies evaluating penile length maintenance post-prostatectomy have utilized a vacuum erection device with varying rates of efficacy. However, to date, no studies have evaluated the benefits of using PTT in this clinical setting. The objective of the current study is to evaluate the efficacy of a novel, Mayo-clinic developed PTT device in maintaining (randomized phase) or restoring (open label phase) reduced penile length.

1.2 Investigational Device

RestoreX is a PTT device developed by PathRight Medical using technology licensed from the Mayo Clinic. The device is classified as class I (orthotic) and does not require clinical trials to prove safety or efficacy. Mayo Clinic is currently conducting a randomized clinical trial to evaluate several clinically relevant factors including safety, comfort, and preference and to provide preliminary data on dosing and efficacy (IRB 17-001283).

The device has two functional aspects. The first is the ability to provide direct traction on the penis. The second is the ability to provide counter-bending forces, to treat conditions such as Peyronie's disease (bent penis). In the current study, only the direct traction aspects of the device will be investigated.

Men randomized to treatment will be recommended to utilize the device for 5 months for 30 minutes, once daily, 5 days per week or 30 minutes, twice daily, 7 days per week after undergoing a prostatectomy.

After the initial randomized phase, all patients will enter an open-label phase where they may use the device as little or as much as they choose for a period of 6 months.

1.3 Preliminary Data

Currently, there is a small amount of preliminary data available on the RestoreX® instrument. During the developmental phase of the device, a quality improvement project was performed to evaluate the clamping portion. It was determined that the clamp represented the most critical aspect of the device, as this was where the majority of discomfort occurred with other devices. Additionally, the clamp needed to provide sufficient friction to allow adequate traction without having the glans of the penis dislodge from the device.

A total of 15 patients participated in the quality improvement project and had the clamps applied under direct supervision for 30 minutes. After the 30 minutes, all patients reported 0/10 pain, and only minimal transient erythema was documented by the physician. The clamp was again applied, and traction forces were administered to determine if the clamp was able to remain intact despite stretching forces applied. This also resulted in a successful outcome, with all patients able to successfully achieve a minimum required tension of 1 kg, with a 36% safety factor achieved before any discomfort was reported among any patient. During the testing, patients reported improved comfort with the use of a wrap such as gauze or Coban, which permitted additional traction in all patients.

Regarding background data on the RestoreX device, currently, Mayo Clinic is conducting a randomized clinical trial evaluating its role in men with PD (IRB 17-001283). Initial data are expected by the end of 2018.

1.4 Study Rationale and Risk Analysis (Risks to Benefits Ratio)

1.4.1 Study Rationale

PTT has been shown to improve penile length in several clinical scenarios, including following penile surgery, as a primary lengthening therapy, and in men with conditions which shorten the penis such as Peyronie's disease. To date, no studies have evaluated the role of PTT in maintaining and restoring penile length in men undergoing prostatectomy for prostate cancer. The current study is designed to address this gap in the literature.

1.4.2 Potential Benefits

There are several potential benefits to using PTT following prostatectomy. As loss of penile length results in several issues including loss of sexual function, cosmetic concerns, and difficulty in maintaining hygiene (incontinence resulting in yeast infections), the ability to maintain or restore length post-prostatectomy may mitigate these issues. Additionally, following prostatectomy, an increased percentage of men experience penile curvature (Peyronie's disease [PD]), which can be both functionally and psychologically distressing.

PTT has previously been demonstrated to limit the extent of penile curvature that men experience among those with early PD, and therefore, the use of PTT early in the post-prostatectomy phase may reduce the likelihood of either developing the condition or in lessening the extent of the condition. It is not expected that the use of PTT will impact (improve or worsen) erectile rigidity post-prostatectomy or impact orgasmic or ejaculatory dysfunctions.

1.5 Anticipated Duration of the Clinical Investigation

The overall study will be scheduled for 3 years, to permit adequate time for enrollment and follow-up. The intervention phase will include 5 months of randomized treatment (for the treatment arm), 3 months of open label treatment (for all arms) and up to 12 months post-prostatectomy follow-up.

2 Study Objectives

2.1 Primary Objective

1. The primary objective is to assess penile length pre and post completion of RestoreX® traction therapy compared to control groups (no treatment) of subjects who have undergone a prostatectomy.

2.2 Secondary Objectives

1. Compare patient compliance with traction device.
2. Compare patient reported satisfaction with use of traction device.
3. Evaluate any adverse events (AEs) with use of RestoreX® for penile lengthening.
4. Compare the rate of Peyronie's disease development among groups
5. Compare patient satisfaction scores including satisfaction with overall penile length.
6. Evaluate and compare patient erectile function among groups
7. Compare penile length outcomes pre- and post-open phase traction therapy
8. Evaluate the duration of treatment utilized during the open phase of treatment
9. Review associations between pre-surgical factors (demographics, disease-specific factors, and standardized questionnaires) and outcomes

3 Study Design

3.1 Subject Selection

3.1.1 Inclusion Criteria

- Undergoing prostatectomy
- >18 years old
- Seen in the post-prostatectomy rehab clinic

3.1.2 Exclusion Criteria

- Urethral complications from prostatectomy at the time of baseline visit
 - Complications include contrast extravasation, anastomotic dehiscence of vesicourethral anastomosis, need for re-doing of vesicourethral anastomosis intra-operatively

3.2 Setting

The current study will be conducted at the Mayo Clinic in Rochester, MN Department of Urology. All patients will be recruited from the post-prostatectomy rehab clinic.

3.3 Recruitment

Patients attending the post-prostatectomy rehabilitation clinic will be notified of the study and offered participation if meeting inclusion / exclusion criteria. Patients will then be given up to one month post-prostatectomy to decide whether or not they would wish to enroll. Those interested in proceeding with the trial will be invited to meet with a study coordinator. At this time, the details of the study itself will be reviewed with the potential participant. No financial incentives will be provided to participate in the trial; however, participants would be given a RestoreX® device at no charge. Patients will not be charged for any visits related to the study, and no labs or other testing will be obtained which require payment.

Patients will also be provided with a recruitment flyer by the physician, resident or physician assistant they are seeing during their standard clinic appointment prior to their prostatectomy procedure. This provides patients with additional time to consider the research study. Those interested will be encouraged to reach out to the study coordinator for additional information.

3.4 Consent and Enrollment

Patients attending a penile rehabilitation clinic (either prior to or following surgery) will receive a description of the study. Those interested in participating, will be given the opportunity to meet with the study coordinator to further review study details and formal consent.

Patients that would like additional time to consider their participation will be given another opportunity to meet with the study coordinator up to one month following the prostatectomy.

If the patient expresses interest in participating at any of these times, a formal consent will be reviewed (see **Attachment – Consent Form**).

At enrollment, all participants will be assigned a study identifier, with a master list maintained in a password protected database (Mayo server) linking the patient to the identifier. A total of 30 patients will be enrolled into each arm of the study, for a total of 90 patients enrolled overall. It is estimated that 100 patients will need to be screened to enroll the 90 patients.

3.5 Study Schema

Prior to surgery, data will be recorded by the surgeon using the current standard of care questionnaires (EPIC-50, IIEF-15 disease specific variables, and demographics).

Following surgery, patients will be seen in the clinic based on the standard routine clinical practice for their catheter removal (approximately 1-3 weeks post-prostatectomy). At this time, and after the patient has consented, they will undergo initial study penile length assessments (described later in the protocol) and be educated on how to use the device properly by a trained nurse. Patients will then be given a baseline questionnaire to complete. In some cases, patients may not have been provided the IIEF-15 questionnaire prior to surgery. For these patients that have not yet filled out this questionnaire and had their data recorded in their records, they will instead receive the IIEF-15 questionnaire during this baseline visit.

Once consent and study assessments are completed, the patients will be randomized into one of three groups:

1. PTT for 30 min 1x/day, 5 days/week
2. PTT for 30 min 2x/day, 7 days/week
3. Control (no treatment)

Patients in the treatment arm will record a daily journal of their usage of the device. Patients will then begin using the device 4 weeks after surgery as instructed for the times appropriate to their group. This ensures adequate time for the patient to recover from their procedure before beginning to use the device. The study coordinator will call the patient to remind them to begin using the device.

After 5 months of using the device (+1.5 months permitted), patients will return for subsequent assessments (see below) and a follow-up questionnaire. At this time, patients will be encouraged to report any adverse events. They will also be requested to bring their device back to the clinic to review proper usage and any questions on the device. After completion of the subsequent assessments, patients will begin a 3-month, open-label phase of the trial. During this period, the patients will be allowed to use the device for 30 minutes at a time, with a frequency to be determined by the patient.

After completion of the 3-month open-phase portion of the trial, patients will return to the clinic to undergo final assessments, which are identical to the 6-month assessments. Patients will then be encouraged to self-report any additional adverse events (AE's) that they encounter over the subsequent 6 months.

Since participants are being asked to travel to Mayo Clinic for subsequent assessments, we will provide a remuneration amount of up to \$600. The purpose is to assist participants in their travel to and from Mayo Clinic. Those that provide consent will be provided \$100 after their baseline assessment. After their second visit, 6 months post-procedure, they will receive \$250. After their third visit, 9 month post-procedure, they will receive \$250.

If patients are unable to travel back to Mayo Clinic for their 6 and 9 month follow up visit, but are still willing to participate in the study, we will ask them to complete the 6 and 9 month questionnaires via letter mail and return it to Mayo Clinic along with their usage diary.

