3.6 Randomization Protocol

Following enrollment and completion of the initial length assessment, patients will be categorized into the appropriate strata based on their baseline stretched penile length; strata categorized as <10 cm, 10cm-13cm, 13.1cm-16cm, >16cm stretched length. Each stratum will have a separate randomization table provided such that one of three possible outcomes will occur no less frequently than every other case. This is done to better account for baseline variables that may impact outcomes and to assist with matching groupings appropriately.

The explanation of which grouping the patient is assigned will then be reviewed, and if the patient subject is assigned to the treatment group, a RestoreX® device will be provided.

4 Study Procedures

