4.2 Baseline Assessment

- Participant consented (if they were not originally consented at the pre-operative appointment)
- Obtained prior to randomization at time of catheter removal (part of standard care)

- Objective assessments
 - Penile length – measured from pubic symphysis to glanular corona
- Subjective questionnaires (attached)
 - Disease specific history
 - IIEF-15 (for patients who have not completed pre-operatively)
- Device usage diary provided for treatment group

4.3 6 Month Visit

- Penile length assessment
- Questionnaires (attached)
 - 6 month
 - IIEF-15
- Device usage diary retrieved from treatment group
- Device usage diary given to all participants (enter open label phase)

4.4 9 Month Visit

- Penile length assessment
- Questionnaire
 - 9 month
 - IIEF-15
- Retrieve device usage diary

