8.4 Regulatory Information

PathRight Medical has registered the RestoreX® device with the FDA as a Class I device, similar to limb orthotics (see Attachment – RCRI Position Paper). The device is available without a prescription and may be purchased by the general public. As such, clinical studies are not required prior to its routine use, and the current studies are being done as an investigator-initiated project to determine its potential role in length of penile prosthesis inserted.

9 References

1. Trost, L. W., Munarriz, R., Wang, R. et al.: External Mechanical Devices and Vascular Surgery for Erectile Dysfunction. *J Sex Med*, **13**: 1579, 2016

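### As worded, section 3.5 teaches all consented men to use the traction device before randomisation, future no-treatment controls included, which adds an avoidable and unrecorded risk of control-arm traction use

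*Combined protocol and SAP*

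**What the plan says.** Section 3.5 (Study Schema) describes the catheter-removal visit, about 1 to 3 weeks after surgery, in this order.

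- Consent and length: "At this time, and after the patient has consented, they will undergo initial study penile length assessments".
- Teaching: the same sentence continues that they will "be educated on how to use the device properly by a trained nurse".
- A baseline questionnaire follows.
- Allocation: "Once consent and study assessments are completed, the patients will be randomized into one of three groups". Two groups use traction on different schedules and the third receives no treatment.

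Other sections bear on the point.

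- Section 3.4: "A total of 30 patients will be enrolled into each arm of the study, for a total of 90 patients enrolled overall".
- Section 3.6, after allocation: "if the patient subject is assigned to the treatment group, a RestoreX® device will be provided". This limits supply of the device by arm. It does not mention teaching.
- Section 4.2: "Device usage diary provided for treatment group". Section 4.3 retrieves that diary from the treatment group at 6 months and only then gives a diary to everyone, for the open-label phase.
- Section 8.4: "The device is available without a prescription and may be purchased by the general public".
- Section 3.3 promises participants a device free of charge, and section 8.3 lets them keep it.
- Section 3.5 also lets men who cannot travel return the 6- and 9-month questionnaires by mail.

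**The concern.** The primary objective (section 2.1) compares penile length after traction with length in untreated men. That contrast depends on controls staying off traction for the 5-month randomised phase. Practical instruction before allocation gives future controls a skill they are not meant to use until the open-label phase, for a product on open sale.

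The visible text contains no counterweight. The eligibility criteria (3.1) do not mention outside traction use, no section asks controls to refrain from it, and the controls keep no diary before 6 months. The three analysis sets in section 5.2 are defined by failure to use the device as recommended; none deals with controls who use one. If some controls did use traction, the length difference would shrink and the diary data could not show why.

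**Working it through.** **Who is taught, and when.** The subject of the teaching clause is the consented patient, the same subject as for the length measurement. No arm is named, and at that point in the sequence no man has an arm. The questionnaire and then randomisation follow. Controls are 30/90 = one third of the men, so about 30 future controls fall under the clause.

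**What is restricted by arm.**

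| Item | Section | Restricted to traction arms before 6 months? |
|---|---|---|
| Device supply | 3.6 | Yes |
| Usage diary | 4.2, 4.3 | Yes |
| Teaching | 3.5 | No, as worded |
| Purchase outside the trial | 8.4 | No; on open sale |

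So the one item given to controls before allocation is the instruction, and the one tool that would record use is withheld from them.

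**Direction of the bias.** Let D be the true traction-versus-control difference, and c the fraction of controls who use a device and gain its full effect. The control mean moves by cD towards the traction mean, so the expected contrast is D − cD = (1 − c)D.

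**Illustrative size.** The documents give no value for c, so the range below is an assumption. It covers contamination from every cause, not just early teaching. The plan states no alpha, power, effect size or SD, so the 90 cannot be reproduced by a sample-size formula. For scale only, suppose two-sided alpha 0.05 and a true effect that would give 80% power without contamination. With 30 controls this means:

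- 30 v 30: d = (1.960 + 0.842) × √(1/30 + 1/30) = 0.72
- 60 v 30 (both traction arms pooled): d = 2.802 × √(1/60 + 1/30) = 0.63

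In both cases, power under contamination ≈ Φ(2.802(1 − c) − 1.960).

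| c (assumed) | Retained effect, 1 − c | Power, from an assumed 80% |
|---|---|---|
| 10% | 90% | 71% |
| 20% | 80% | 61% |
| 30% | 70% | 50% |

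These figures apply only to traction-versus-control contrasts. A comparison of the two traction schedules does not involve controls.

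**The case against.** **The order rests on loose prose.** Section 3.5 also has patients begin using the device 4 weeks after surgery and bring it back at the 6-month visit, again without naming an arm, although controls have not been issued one. The stated preconditions for randomisation are consent and assessments (3.5) and the initial length measurement (3.6); neither names teaching. The baseline list (4.2) and the schedule (4.6) omit it. A reader might infer that the plan firmly requires every man to be trained first, and the documents do not support that degree of certainty. What remains is that the only text placing the teaching puts it before allocation. The other loose sentences come after allocation, where an arm can be understood from context. At the least the order needs clarifying.

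**Teaching is not the main source of the risk.** All men hear about the device through the study description, the flyer and consent, and it is on open sale in any case. A control who expects a free device and an open-label phase has less reason to buy one. This stands. Teaching adds to an existing risk by an unknown amount.

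**Unseen attachments may help.** The consent form and 6-month questionnaire are not shown. Either might restrict or ask about outside traction. This stands too, so the gap is in the visible text and the diary, not proven for the whole trial.

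**The dilution figures can be over-read.** A reader might turn them into an effective trial size, 90 × (1 − c)², giving about 73, 58 and 44 men. That is not supported. Only contrasts with control are diluted, a single traction arm against control involves 60 men and not 90, full effect in every crossover is assumed, and moving the session would not bring c to zero.

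**Moving the session has costs.** Controls followed up by mail would lose their only scheduled in-person teaching, and staff contact at baseline would differ by arm. The first needs a remedy. The second is a small addition, since the traction arms already differ from control by device, diary and reminder call.

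**Conclusion.** The point holds as an avoidable weakness in wording and sequence. Taken as written, section 3.5 trains about 30 future controls on a device they can buy, and the randomised-phase diary would not capture their use. Any resulting bias runs towards no difference in the primary contrast. Its size is unknown: the retained effects of 90%, 80% and 70% illustrate total contamination of 10%, 20% and 30% with full effect, and are not estimates of what early teaching causes.

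Two stronger conclusions are not supported. One is that contamination will occur or will be large; the documents give no rate, and the free device and open-label phase work against it. The other is that control use cannot be detected at all; the 6-month questionnaire might ask.

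Confidence is moderate. The conclusion assumes that section 3.5 is followed in the order in which it is written. The change is worth making because it protects the primary comparison at almost no cost.

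**What to change.** 1. In section 3.5, place device teaching after randomisation. Give it to the two traction arms when the device is handed over under section 3.6.
2. Teach controls at open-label entry, after the 6-month length measurement. This also brings their instruction close to the time when they may use the device.
3. For controls who follow up by mail, provide remote instruction at open-label entry, once the 6-month questionnaire has been returned.
4. Add teaching to sections 4.2 and 4.3 and to the schedule in 4.6, by arm, so that the sections agree.
5. At 6 months, ask all arms, by mail where needed, whether and how often they used any traction device not supplied by the study since baseline, including a privately bought one. Report the answers by arm. Omit this if the existing questionnaire already asks.

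Cost: a wording change, one added question, and a remote training option for controls who do not attend at 6 months. The teaching itself is the same; only its timing moves.

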4.6 Schedule of Events

Table 1: Schedule of Events

Study Activity	Pre-operative	Baseline Assessment	6 Month	9Month
----------------	---------------	---------------------	---------	--------

		(post-operative up to 1 mo)		
Consent	X	X		
EPIC-50	X			
IIEF-15	X	X	X	X
Disease Specific History		X		
Length Assessment		X	X	X
Patient Diary Provided		X	X	
Questionnaire 6 Month			X	
Questionnaire 9Month				X

5 Statistical Plan

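### The IIEF-15 baseline is pre-operative for some men and completed 1-3 weeks after prostatectomy for others, which mixes two quantities in objective 9 and in any within-patient change

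*Combined protocol and SAP*

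**What the plan says.** All references are to the combined protocol and SAP.

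- **Planned timing.** Section 3.5 opens with "Prior to surgery, data will be recorded by the surgeon using the current standard of care questionnaires", and the IIEF-15 is among the forms named. Section 4.1 lists it under pre-operative assessments.
- **The exception.** Section 3.5 continues: "In some cases, patients may not have been provided the IIEF-15 questionnaire prior to surgery". For those men, "they will instead receive the IIEF-15 questionnaire during this baseline visit". Section 4.2 repeats the rule in its baseline list.
- **When that visit falls.** Section 3.5 places it at catheter removal, about 1-3 weeks after surgery. The schedule in section 4.6 labels the column "post-operative up to 1 mo". It marks the IIEF-15 in both the pre-operative and the baseline column, with no footnote saying that one replaces the other.
- **Intended use.** Objective 6 (section 2.2) compares erectile function among groups. Objective 9 reads: "Review associations between pre-surgical factors (demographics, disease-specific factors, and standardized questionnaires) and outcomes". The Study Summary plans to compare questionnaire answers between groups and across the occasions on which they are collected.
- **Analysis.** Section 5.2 mentions questionnaire responses only in general terms. It has no rule to record, separate, adjust for or exclude by the timing of the IIEF-15.

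**The concern.** The two possible forms lie on either side of the operation, and section 1.1 says what the operation can do to the score: "The treatment of prostate cancer results in several known sexual dysfunctions, including erectile dysfunction". A man who completes the form two weeks after prostatectomy, with no instruction about the period he should have in mind, may well report his function since surgery. His score then measures something different from that of a man who completed the form beforehand.

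Two uses are exposed. In objective 9 a post-operative score would stand as a pre-surgical predictor, which it is not. Randomisation does not help, because this is an association analysis and not a comparison of arms. In a within-patient comparison over time, the loss from before surgery to 6 or 9 months would be understated for men whose starting score already contains part of that loss. A late form given without an instruction cannot be corrected afterwards, so the matter has to be settled before data collection.

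**Working it through.** The plan states no figure on this point, so there is nothing to reproduce. The check is first one of consistency and then an illustration of size.

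**Consistency.** Under section 3.5 the late form takes the place of the missing pre-operative one. Under objective 9, standardized questionnaires are pre-surgical factors. A form about current function completed after surgery satisfies the first rule but not the description in the second. Nothing in section 5.2 resolves this.

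**Inputs.** From the documents: 30 men per arm, 90 in all (section 3.4), and randomisation stratified by stretched length only (section 3.6). Not in the documents, and therefore assumed: the share q of men with a late form (0.1 to 0.5), and the mean gap D between pre- and post-operative scores, in units of the pre-operative SD (0.5 to 2).

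**Shift in mean change from baseline** = q × D.
- Low end: 0.1 × 0.5 = 0.05 SD.
- q = 0.3, D = 1: 0.3 × 1 = 0.3 SD.
- High end: 0.5 × 2 = 1.0 SD.

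**Variance of the mixed baseline** = (1 − q) + q·s² + q(1 − q)D², where s is the SD of post-operative scores relative to pre-operative ones. With q = 0.3 and D = 1:
- Same spread after surgery (s = 1): 0.7 + 0.3 + 0.21 = 1.21, a rise.
- No spread after surgery (s = 0): 0.7 + 0 + 0.21 = 0.91, a fall.

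The direction therefore depends on how far post-operative scores bunch together, which the documents do not tell us.

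**Correlation with true pre-surgical function.** If surgery lowered every man's score by the same amount, the correlation would be multiplied by 1/√1.21 = 0.91 at q = 0.3 and D = 1. That constant-shift assumption is strong, so the factor is illustrative.

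**Effect on the arm comparison.** Timing is fixed before randomisation, so the expected difference between arms in q is zero. By chance, with 30 v 30 and q = 0.3, that difference has SD √(2 × 0.3 × 0.7 / 30) = 0.118. With D = 1, an unadjusted comparison of change scores between two arms carries an artefact with mean zero and SD 0.118 × 1 = 0.12 SD. A comparison of 6-month scores alone carries none.

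**The case against.** The strongest reply is that the plan never says it will do the harmful thing. It defines no IIEF-15 change endpoint and no single pooled baseline. Objective 6 can be met by comparing 6-month scores between arms, with no baseline form at all. The schedule keeps the two occasions in separate columns, so an analyst could use only pre-operative forms for objective 9. The form given at catheter removal is in an attachment not available for review, and it may already ask about function before surgery. Erectile function is a secondary matter, and section 1.4.2 expects no effect of traction on rigidity. Because men may enrol up to a month after surgery, some fallback is unavoidable.

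Most of this stands as a limit on the point. A reader might infer that both forms are pooled as the baseline for objective 6; the documents do not say so. A reader might also infer that the treatment comparison is biased; it is not, because timing precedes randomisation. Nor can one claim that baseline variance must rise or that associations must shrink. The first depends on post-operative spread, and the second could also be disturbed if men who lack a pre-operative form differ in outcome.

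What does not fall is the rule itself. It substitutes a post-operative form, objective 9 calls such questionnaires pre-surgical, the Study Summary compares across time points, and no text keeps the two kinds of form apart. An instruction in the attachment would reduce the problem but would still leave recalled scores mixed with prospective ones.

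**Conclusion.** The point holds for objective 9 and for any within-patient change in IIEF-15, and it should be corrected. It does not reach the randomised comparison of 6-month scores or the primary length outcome, neither of which is biased by the timing of this form.

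Its size cannot be computed from the documents, which say only that some men are affected. The 0.3 SD shift at a 30% share and a 1 SD gap, and the range of 0.05 to 1.0 SD, are illustrations that rest on assumed inputs. The conclusion also assumes that the late form carries no instruction to recall the period before surgery. This is true of the protocol body but could not be checked in the attachments.

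**What to change.** 1. Give the IIEF-15 before surgery to every man approached at that stage.
2. When it is first given at catheter removal, instruct the man to answer for the period before surgery. Record the completion date and whether the form is pre-operative or late, and footnote the schedule in section 4.6 accordingly.
3. For objective 9 and within-patient change, use only true pre-operative forms in the main analysis and add late forms in a sensitivity analysis.
4. For objective 6, compare 6-month scores between arms, adjusting for baseline score and a timing indicator. A baseline-by-timing interaction is not advised: at an assumed 30% share only about 0.3 × 30 = 9 men per arm would have late forms.

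The cost is one line of instruction, one recorded variable and a few sentences in section 5.2. The downsides are recall error in the late forms and a smaller main analysis for objective 9: of 90 men, 81 would remain at an assumed 10% share and 63 at 30%, before any other loss.
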